#### **12.2.2 Handling BLQ Values**

The following procedures will be used for plasma concentrations below the lower limit of quantification (LLOQ) (reported as not quantifiable [NQ]):

- Plasma samples that are BLQ are reported as zero on the data listings.
- Samples that are BLQ are treated as zero in the calculation of summary statistics (eg mean, SD, etc.) for the plasma concentrations at individual time points.
- Mean concentrations are reported as zero if all values are BLQ, and no descriptive statistics are reported. If the calculated mean ( $\pm$  SD) concentration is less than the LLOQ, the value will be reported as calculated. The mean values derived using these conventions will be used to create the mean plasma concentration versus time plots.
- For calculation of area under the plasma concentration curve (AUC), BLQ values are set equal to zero in the dataset loaded into WinNonlin for pharmacokinetic analysis. WinNonlin uses the zero values that occur before the first time point with a concentration greater than LLOQ, but WinNonlin excludes the zero values from the AUC calculation for all later time points.

#### **12.2.3 Pharmacokinetic Parameters**

##### **Part 1**

The PK analysis for Part 1 will be conducted by the Clinical Pharmacology and Pharmacokinetics Department of Shire Pharmaceuticals or its designee using WinNonlin Phoenix version 6.2 or higher (Pharsight Corporation, Mountain View, California, USA).

PK parameters will be determined from the plasma concentration-time data for lanthanum by non-compartmental analysis. All calculations will be based on actual sampling times.

The PK parameters will include, but not be limited to:

- $C_{\max}$  Maximum concentration occurring at  $t_{\max}$
- $t_{\max}$  Time of maximum observed concentration sampled during a dosing interval
- $AUC_{0-\infty}$  Area under the curve extrapolated to infinity, calculated using the observed value of the last non-zero concentration
- $AUC_{\text{last}}$  Area under the curve from the time of dosing to the last measurable concentration
- $AUC_{0-48}$  Area under the curve over the interval from dosing to 48 hours post-dose
- $t_{1/2}$  Terminal half-life
- $\lambda_z$  First order rate constant associated with the terminal (log-linear) portion of the curve
- $CL/F$  Total body clearance for extravascular administration divided by the fraction of dose absorbed
- $V_z/F$  Volume of distribution associated with the terminal slope following extravascular administration divided by the fraction of dose absorbed.

### Parts 2 and 3

The PK analysis for Parts 2 and 3 will be conducted by a vendor that specializes in population PK analysis.

Plasma concentration-time data for Part 2 treatment period 2, and Part 3 will be combined with those from Part 1 and subjected to population PK analysis using NONMEM to determine estimates of steady-state systemic exposure ( $C_{\max}$ , minimum plasma concentration and area under the plasma concentration-time curve at steady-state) and relationships of systemic exposure to dose and to safety findings explored if appropriate.

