**Part 2b:** Subjects will begin 8 weeks of treatment with lanthanum carbonate. Lanthanum carbonate will be mixed with food and given 3 times a day. If the subject has only 2 meals a day the lanthanum carbonate dose will split equally across the 2 meals with a single dose not exceeding 1000mg. The starting total daily dose of lanthanum carbonate is 1500mg for all subjects. The total daily dose will be titrated 2-weekly, as appropriate, until the target serum phosphorus level is achieved, or until a maximum daily dose of 3000mg is reached. Once serum phosphorus control is achieved or the maximum dose is reached, the dose of lanthanum carbonate will be maintained until the end of the 8-week treatment period. All new subjects will be enrolled in Part 2b only under Version 6.0 of the protocol.

**Part 3:** Subjects who complete participation in Part 2 (2a or 2b) may continue to receive lanthanum carbonate for an additional 6 months (including subjects who participated in Part 2a, Treatment Period 1/calcium carbonate treatment arm, but who discontinued due to hypercalcemia). The dosage of lanthanum carbonate will be determined by the Investigator based on serum phosphate levels taken at each study visit up to a maximum dose of 3000mg/day.

**Safety Follow-up:** A safety follow-up telephone call will be made to all subjects or their parent/legally authorized representative (LAR) 7-14 days following the last dose. In the event of early discontinuation due to kidney transplantation, the safety follow-up call will be 30±7 days from the last dose.

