#### **Pharmacokinetics:**

Blood samples for pharmacokinetic evaluation will be collected during all 3 study periods (Parts 1, 2, and 3). Plasma lanthanum concentrations will be determined by a previously validated method utilizing inductively coupled plasma mass spectrometry.

Part 1. Blood samples for determination of single-dose lanthanum pharmacokinetics will be collected pre-dose and at 3, 5, 6, 8, 12, 24, and 48 hours after dosing. Plasma lanthanum concentrations will be analyzed by non-compartmental methods to determine pharmacokinetic parameters including, but not limited to,  $AUC_{0-t}$ , area under the plasma concentration-time curve from time zero to 48 hours ( $AUC_{0-48}$ ),  $C_{max}$ , time to  $C_{max}$ , and, if appropriate, apparent terminal half-life ( $t_{1/2}$ ) and apparent terminal-phase disposition rate constant ( $\lambda_z$ ) and area under the plasma concentration-time curve from time zero to infinity ( $AUC_{0-\infty}$ ).

Summary statistics (number of observations, mean, standard deviation, coefficient of variation, median, maximum, minimum, and geometric mean) will be determined for all pharmacokinetic parameters.

Part 2 (Part 2a (Treatment Period 2) and Part 2b) and Part 3. Pharmacokinetics will be evaluated during lanthanum carbonate dosing using a sparse sampling approach. Blood samples (at least 2 per subject) for pharmacokinetic assessments will be collected during Parts 2a (Treatment Period 2), 2b and 3 from defined time-windows (to be selected from: 0-2 hours, 2-4 hours and 4-6 hours, after the first dose/meal of the day, so as to cover the full dosing interval). Plasma concentration-time data for Parts 2a (Treatment Period 2), 2b and 3 will be combined with those from Part 1 and subjected to population pharmacokinetic analysis using NONMEM software to determine estimates of steady-state systemic exposure ( $C_{max}$ ,  $C_{min}$  [minimum plasma concentration], and area under the plasma concentration-time curve at steady-state) and relationships of systemic exposure to dose and to safety findings explored if appropriate.

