**Table 3: Schedule of Assessments for Part 2b and Part 3**

	Part 2b (Visit window ±3 days)				Part 3 (Visit window ±1 week)		
Visit	1.0a	Washout W1b	2.1-2.3	2.4	3.0-3.4	3.5/End of Studyc	Safety Follow-up callj
Week	0	0-3 weeks duration	2, 4, 6d	8d	12, 16, 20, 24, 28	32d	33-34d

d Visit weeks may be variable depending on duration of washout (+3 weeks).

e Local laboratory assessments for phosphorus in Part 2b are for titration purposes, as required, and will not be analyzed; data from Visits 3.0-3.4 will be collected and assessed.

f Visit 2.2 only; Each subject will have at least 2 samples taken for pharmacokinetic assessment. These should be taken during defined time windows (to be selected from: 0-2 hours, 2-4 hours and 4-6 hours, after the first dose/meal of the day). Note: If the sampling is not done at Visit 2.2, blood sampling for pharmacokinetics must be taken at an alternative visit during Part 2b.

g Visit 3.3 only; Each subject will have at least 2 samples taken for pharmacokinetic assessment. These should be taken during defined time windows (to be selected from: 0-2 hours, 2-4 hours and 4-6 hours, after the first dose/meal of the day). Note: If the sampling is not done at Visit 3.3, blood sampling for pharmacokinetics must be taken at an alternative visit during Part 3.

h Investigational product will be dispensed at Visit 1.0 if eligible, however if a washout is required then investigational product will be dispensed at visit W1.

i For subjects entering Part 3 only.

j Safety follow-up call to be made 7-14 days following last dose of investigational product. For subjects discontinued due to kidney transplantation, the safety follow up call to be made 30 ± 7 days from the last dose.

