## 9.12 Other Analyses

### 9.12.1 Pharmacokinetic Analyses

#### Part 1

Plasma lanthanum concentrations will be analyzed by non-compartmental methods to determine pharmacokinetic parameters including, but not limited to, area under the plasma concentration-time curve from time zero to the time of the last quantifiable concentration ( $AUC_{0-t}$ ), area under the plasma concentration-time curve from time zero to 48 hours ( $AUC_{0-48}$ ),  $C_{max}$ , time to  $C_{max}$ , and, if appropriate, apparent terminal half-life ( $t_{1/2}$ ) and apparent terminal-phase disposition rate constant ( $\lambda_z$ ) and area under the plasma concentration-time curve from time zero to infinity ( $AUC_{0-\infty}$ ).

Summary statistics (number of observations, mean, standard deviation, coefficient of variation, median, minimum, maximum, and geometric mean) will be determined for all pharmacokinetic parameters.

## Parts 2 and 3

Plasma concentration-time data for Part 2a (Treatment Period 2), Part 2b, and Part 3 will be combined with those from Part 1 and subjected to population pharmacokinetic analysis using NONMEM to determine estimates of steady-state systemic exposure ( $C_{\max}$ , minimum plasma concentration [ $C_{\min}$ ] and area under the plasma concentration-time curve [AUC] at steady-state) and relationships of systemic exposure to dose and to safety findings explored if appropriate.

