## **1. INTRODUCTION**

This statistical analysis plan (SAP) provides a technical and detailed elaboration of the statistical analyses of efficacy, safety, and pharmacokinetic data as described in the final study protocol version 6.0 dated 18 Oct 2016 incorporating most recent amendment #5. Specifications for tables, figures, and listings are contained in a separate document.

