## 2.3 Blinding

This is an open-label study; the study includes only 1 sequence in Part 2, (calcium carbonate for the treatment period 1 and lanthanum carbonate for the treatment period 2). Blinding is not applicable.

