### **Part 2a (Treatment Period 2), Part 2b and Part 3 Combined (Lanthanum Carbonate only):**

A summary table will be produced showing the number and proportion of subjects in Safety Analysis Set 2 who completed the study, who entered Part 3 due to hypercalcaemia during treatment with calcium carbonate in Part 2a (Treatment Period 1), subjects in the FAS, PP2, SCS Set and subjects who prematurely discontinued from the study (also split by reason for withdrawal). (**Table 1.1.3.1**) This summary table will also be presented by age group ( $\geq 10$  to  $<12$  years,  $\geq 12$  to  $<18$  years). (**Table 1.1.3.2**)

An enrolment summary will be presented by site, and by country, showing the first day of consent, and the last study completion/withdrawal date among all Enrolled Subjects, the duration of enrolment (in days) [calculated as (last date of contact for any subject at that site - the first date of informed consent for any subject at that site + 1)], and the number of subjects enrolled and in each subject population set. The number and proportion of subjects enrolled in total, by site, and by country will be summarised. For individual sites, the site location and primary investigator's name will also be presented. (**Table 1.1.4**)

A listing of all Screen Failures (ie, subjects who gave informed consent and failed to meet the inclusion and/or met at least 1 of the exclusion criteria and were not administered IP(s) as defined by the protocol) will be presented along with reasons for screen fail and details of any adverse events (AEs).

A listing of subject disposition (**Listing 1.1**) will be provided for all Enrolled Subjects, including the date of informed consent/assent, date of first dose and date of last dose for each part of the study (Part 1, Part 2, and Part 3) and each treatment group, accordingly (Part 2a: Calcium Carbonate, Part2a: Lanthanum Carbonate), date of completion/discontinuation, and whether the subject completed the study. Details of early terminations will also be listed for all Enrolled Subjects including the date of informed consent/assent, date of first dose and date of last dose for the part of the study (Part 1, Part 2, or Part 3) and treatment group, accordingly (Part 2a: Calcium

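### The SAP's list of population-PK data sources does not name Part 2b, although the protocol includes it and the SAP declares no change

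*SAP*

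**What the plan says.** The SAP states that it elaborates the "final study protocol version 6.0 dated 18 Oct 2016 incorporating most recent amendment #5". Under that version, "All new subjects will be enrolled in Part 2b only under Version 6.0 of the protocol".

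Protocol section 9.12.1, Parts 2 and 3, gives the population-PK input as: "Plasma concentration-time data for Part 2a (Treatment Period 2), Part 2b, and Part 3 will be combined with those from Part 1". The protocol synopsis, under Pharmacokinetics, agrees: "Plasma concentration-time data for Parts 2a (Treatment Period 2), 2b and 3 will be combined with those from Part 1".

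SAP section 12.2.3, Parts 2 and 3, gives: "Plasma concentration-time data for Part 2 treatment period 2, and Part 3 will be combined with those from Part 1". Part 2b is not mentioned. The same section says that a vendor specializing in population PK will do the analysis.

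Table 3, which appears in both documents, schedules PK sampling in Part 2b. Footnote f reads: "Visit 2.2 only; Each subject will have at least 2 samples taken for pharmacokinetic assessment". If that visit is missed, the samples are to be taken at another Part 2b visit. Footnote g schedules at least 2 further samples at Visit 3.3.

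**The concern.** The SAP and the protocol give different data sources for the same analysis, and the SAP does not record the difference. The part left unnamed is the one that every new subject enters under version 6.0.

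Both documents give the absence of lanthanum data in patients under 18 as the reason for collecting PK. The pooled analysis is where steady-state maximum and minimum concentration and exposure are estimated, and where any link between exposure and safety would be explored. If the sentence were applied as it stands, samples drawn from children for this analysis would not enter it.

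**Working it through.** The plan states no figure to reproduce. The check compares texts and then counts scheduled samples.

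**1. Data sources side by side**

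| Source of concentrations | Protocol synopsis and 9.12.1 | SAP 12.2.3 |
|---|---|---|
| Part 1 | yes | yes |
| Part 2a, Treatment Period 2 | yes | yes (as Part 2 treatment period 2) |
| Part 2b | yes | not named |
| Part 3 | yes | yes |

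**2. Can the SAP phrase cover Part 2b?** SAP section 2.3 explains the two periods of the single sequence as "calcium carbonate for the treatment period 1 and lanthanum carbonate for the treatment period 2". SAP section 2.1 uses the same label and says that this sequence is now Part 2a. Part 2b is 8 weeks of lanthanum only, so it has no second period. Where the SAP pools lanthanum data and means to include Part 2b, it names it, as in section 5: "Part 2a (Treatment Period 2), Part 2b and Part 3 Combined (Lanthanum Carbonate only". It also names Part 2b for the Per-protocol Set 2 baseline summaries in section 7. On its ordinary meaning in this SAP, the phrase in 12.2.3 does not reach Part 2b.

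**3. Is the difference declared?** SAP section 12.7, on PK departures from the protocol, covers only the definitions of Pharmacokinetic Sets 1 and 2. SAP section 17 has no item on population-PK data sources.

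**4. Does the analysis set settle it?** SAP section 12.3 assigns the Parts 2 and 3 PK analyses to Pharmacokinetic Set 2. Section 12.1 defines that set as members of either Safety Analysis Set with at least one measurable post-dose concentration. A Part 2b subject whose only measurable concentrations come from Visit 2.2 qualifies. The set selects subjects and 12.2.3 selects data, so under a literal reading such a subject would be in the set with no data to analyse. The two sections therefore conflict.

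**5. Samples affected, read literally.** Let a be the number of Part 2b samples and b the number of Part 3 samples for one Part 2b subject. The share left out is a / (a + b). Footnotes f and g set a minimum of 2 at each sampling visit.

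- Minimum at both visits: 2 / (2 + 2) = 2 of 4, or 50%.
- Minimum at Visit 2.2 and 3 samples in Part 3: 2 / (2 + 3) = 40%.
- No Part 3 PK sample, because the subject did not enter Part 3 or stopped before being sampled there: 2 / 2 = 100%.

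The documents do not give the number of Part 2b subjects. As an assumption only, the minimum number of samples left out would be:

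- 5 subjects: 5 × 2 = 10
- 15 subjects: 15 × 2 = 30
- 30 subjects: 30 × 2 = 60

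**The case against.** The best case for leaving the sentence alone is that the SAP as a whole points to inclusion. It elaborates protocol version 6.0, its own Table 3 schedules the Visit 2.2 samples, Pharmacokinetic Set 2 admits Part 2b subjects, and 12.7 records PK departures without listing this one. SAP section 2.3 still describes Part 2 as a single calcium-then-lanthanum sequence, so other text from before Amendment 5 appears to have survived. On this view the phrase in 12.2.3 is a leftover, and nobody decided to drop data.

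That account is plausible, but it is an inference. It explains how the sentence may have arisen without making it correct. A specific data-source rule that disagrees with the protocol and with the SAP's own analysis set still has to be reconciled.

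Two limits on importance stand in full. The one PK objective that names PK parameters, secondary objective 5, concerns a single dose in Part 1. The exposure-safety work is to be explored only if appropriate.

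A reader might also infer that the vendor will build its dataset from this sentence, so that the samples are certain to be lost. The documents do not support that: they say a vendor will do the analysis, but not what specification it will work from.

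**Conclusion.** The SAP sentence is wrong as written. It omits Part 2b from the population-PK data sources, contradicts the protocol in two places, is not declared as a change, and conflicts with Pharmacokinetic Set 2.

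The affected data are the Part 2b samples, at least 2 per subject. At the minimum schedule this is half of the sparse samples for a Part 2b subject also sampled in Part 3, and all of them for one who is not. This assumes that the sentence is applied literally.

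A reader might infer that half of the steady-state information, or some stated amount of precision, is lost overall. The documents do not support that. The 50% figure is per subject and holds only when the counts in the two parts are equal. All Part 1, Part 2a Treatment Period 2 and Part 3 samples stay in the pool, including Part 3 samples from subjects who came through Part 2b. Because the number of Part 2b subjects is not given, the effect on the pooled estimates cannot be calculated.

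The point is confined to the steady-state population-PK analysis. The primary endpoint, the planned safety summaries and the sample size are untouched.

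**What to change.** In SAP section 12.2.3, replace the reference to Part 2 treatment period 2 and Part 3 with Part 2a (Treatment Period 2), Part 2b and Part 3, as in protocol 9.12.1. If a separate specification exists for the population-PK vendor, check that it matches.

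If leaving out Part 2b is intended, list it with a reason in SAP 12.7, and state how Pharmacokinetic Set 2 treats subjects whose only concentrations come from Part 2b.

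Either way the cost is a few words in the SAP. No new data collection, visit or change to the sample size is needed.

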### 12.3 Statistical Analysis of Pharmacokinetic Data

All of the PK analyses for Part 1 will be performed using the Pharmacokinetic Set 1. All of the PK analyses for Parts 2 and 3 will be performed using the Pharmacokinetic Set 2.

Summary statistics (number of observations, mean, standard deviation, coefficient of variation, median, maximum, minimum, and geometric mean) will be determined for all pharmacokinetic parameters by age group for Part 1. Plasma concentrations at each nominal sampling time will also be summarized by age group for Part 1 using descriptive statistics (number of observations, mean, standard deviation, coefficient of variation, median, maximum, and minimum).

#### **12.4 Pharmacodynamic Methods**

Not Applicable.

#### **12.5 Statistical Analysis of Pharmacodynamic Data (if applicable)**

Not Applicable.

#### **12.6 Analyses of Pharmacokinetic/Pharmacodynamic Relationships (If applicable)**

Not Applicable.

#### **12.7 Changes in the Pharmacokinetic or Statistical Methods from Those stated in the Protocol**

The definition of the Pharmacokinetic Set 1 and Pharmacokinetic Set 2 appears as follows in Protocol Version 6.0 (Amendment 5):

Pharmacokinetic Set 1 - Subjects in the Safety Analysis Set 1 for whom the primary pharmacokinetic data are considered sufficient and interpretable. Subjects in Part 1 who vomited may be excluded from Pharmacokinetic Set 1.

Pharmacokinetic Set 2 - Subjects in Safety Analysis Sets 1 or 2 for whom the primary PK data are considered sufficient and interpretable will be included in Pharmacokinetic Set 2

The definition of Pharmacokinetic Set 1 and Pharmacokinetic Set 2 appears as the following in the present SAP for simplification and as a result of standardization of these definitions across studies within Shire:

Pharmacokinetic Set 1 - Subjects in the Safety Analysis Set 1 who have at least 1 measurable post-dose plasma concentration of Lanthanum Carbonate. Subjects in Part 1 who vomited may be excluded from Pharmacokinetic Set 1.

Pharmacokinetic Set 2 - Subjects in Safety Analysis Sets 1 or 2 who have at least 1 measurable post-dose plasma concentration of Lanthanum Carbonate will be included in Pharmacokinetic Set 2.

#### **12.8 Pharmacokinetic References**

Not Applicable.

#### **12.9 Table of Contents for Pharmacokinetic Figures, Tables, and Listings**

Formats and numbering of the tables, listings and figures will be finalized prior to the completion of the Clinical Study Report. No revision to this document is required for changes which do not affect the statistical or PK methods, definitions, or rules defined in this document.

In the event that a limited number of samples yield measurable concentrations, the PK tables, listings and figures will be generated as deemed appropriate. No revision of this document will

be required.

## **TABLES**

PK Tables will be provided by Clinical Pharmacology and Pharmacokinetics Department of Shire Pharmaceuticals or its' designee, as overseen by the pharmacology group.

## **LISTINGS**

PK Listings will be provided by Clinical Pharmacology and Pharmacokinetics Department of Shire Pharmaceuticals or its' designee, as overseen by the pharmacology group.

## **FIGURES**

### **Pharmacokinetic Figures**

PK Figures will be provided by Clinical Pharmacology and Pharmacokinetics Department of Shire Pharmaceuticals or its' designee, as overseen by the pharmacology group.

### **13. OTHER ANALYSES**

Not applicable.

## **14. INTERIM ANALYSIS**

No formal interim analysis is planned for this study. However, a descriptive analysis of efficacy and safety data was produced in Q4 2014 to assist with regulatory interactions as recruitment targets had not been met.

